8 Only performed if a detectable HCV RNA viral load on the Xpert® HCV Viral Load assay is found at a follow-up visit.

4 Schedule of Assessments – Cohort B

Procedure	Screening	Baseline	On-treatment phase		SVR12	Follow-up 1 (SVR24)	Follow-up 2 (SVR36)	Follow-up 3 (SVR48)
			Hospital discharge ¹	End of Treatment				
Study Week	X to 0	0	Variable	4	16	28	40	52
Visit Window (Days)								
Informed consent	X							
Medical history	X		X					
Physical measurements (height and weight)	X							
Liver function tests	X	x		X	X	X	X	X
Full blood count and Biochemistry	X							
HCV RNA testing (local laboratory)	X			X	X	X ⁸	X ⁸	X ⁸
HCV RNA testing (finger-stick capillary whole-blood) ²	X				X	X	X	X
HCV genotyping (local laboratory) ³	X				X ⁸	X ⁸	X ⁸	X ⁸
HIV serology	X							
HBsAg	X							
Clinical assessment (including hepatic decompensation assessment)	X							
Fibrosis assessment (FibroScan or APRI) ⁴	X							
Pregnancy test (females - serum or urine) ⁵	X	X		X				
Treatment initiation		X						
Behavioural survey	X				X			X
EQ-5D-5L	X				X			X
Concomitant medication assessment ⁶	X	X	X	X	X			
Study drug adherence ⁷				X				
D&A evaluation		X		X				
Research Specimen Collection								
DBS Sample for sequencing	X				X ⁸	X ⁸	X ⁸	X ⁸
EDTA Plasma for resistance testing (10mL)					X ⁸	X ⁸	X ⁸	X ⁸

1 End of Treatment visit will be conducted during hospitalisation where possible. If the participant is discharged, whilst on-treatment, End of Treatment will occur at outpatient viral hepatitis services.

2 HCV RNA finger-stick capillary whole-blood will be tested using the Xpert® HCV Viral Load assay on the Gene Xpert® II machine. During follow-up visits (SVR12, SVR24, SVR36 and SVR48), finger-stick capillary whole-blood will be used for HCV RNA and local laboratory HCV RNA may be performed if a positive HCV RNA is detected through the Xpert® HCV Viral Load assay.

3 HCV genotyping will only be performed during follow-up for participants identified with recurrent viraemia

4 Liver fibrosis will be assessed with a FibroScan if possible. Otherwise, an APRI score will be used for fibrosis assessment.

5 Pregnancy testing is not required for females of non-childbearing potential.

6 Concomitant medications will be assessed at Screening and updated at visits as appropriate. During follow-up concomitant medications will only be collected for those related to interactions with treatment of HCV.

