7 Study drug adherence will be collected via telephone on a weekly basis for participants who are discharged prior to treatment completion.

8 Only performed if a detectable HCV RNA viral load on the Xpert® HCV Viral Load assay is found at a follow-up visit.

5 Background and rationale

The excellent efficacy and tolerability of DAA regimens are now widely accepted in diverse patient populations and settings and pave the way for national and global hepatitis C (HCV) elimination policies. Even in populations considered traditionally difficult to treat, such as people who inject drugs (PWID), treatment response rates have been shown to be high and adherence generally good, confirming the rationale behind universal access policies ^{1,2}.

However, whilst studies examining treatment of PWID in settings such as opioid substitution clinics, primary care practices and drug and alcohol treatment services have shown encouraging results, these represent only a selected group already engaged with health care services. A significantly greater challenge is to engage PWID who do not traditionally link to these services in HCV treatment and care. This group is at high risk of morbidity and mortality from co-existing illness and often have competing priorities, as well as being at high risk of ongoing HCV transmission through risk behaviour. To fully address the HCV elimination question, novel ways of engaging these individuals must be sought ³.

Admission to hospital with an injecting related infectious disease (IRID) such as cellulitis, endocarditis, osteomyelitis, occurs far more frequently in people with current injecting drug use than the general population, and of people admitted with IRID up to 75% have a history of HCV infection. Many of these IRID require inpatient management with prolonged intravenous antibiotic or antifungal administration (2-6 weeks).

The period of hospitalisation for management of IRID, particularly when prolonged, may represent an ideal opportunity to engage HCV-infected PWID. The current model of care in which DAA therapy is delayed to be dealt with as an outpatient after discharge is inadequate if high levels of engagement and treatment uptake are to be reached in this population. Given that recent PWID are at high risk of transmission and risk behavior post-discharge, eradication of HCV viremia with successful DAA therapy commenced during hospitalisation may be an important strategy for broader HCV elimination.

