9.2 Visit Schedule

Participants will be invited for Screening whilst they are inpatients of the hospital. Participants will be screened for a detectable HCV RNA using standard HCV RNA assays per their local laboratory and the Xpert® HCV Viral Load assay.

Eligible participants will be treated through standard of care with the applicable treatment regimen as per their enrolled cohort. All participants will commence treatment whilst they are inpatients and subsequent visits whilst on-treatment will be completed during their hospital stay where possible. For participants who are discharged before treatment completion, a hospital discharge visit will be conducted. These participants will continue their on-treatment visits through outpatient viral hepatitis services and receive weekly contact to measure treatment adherence.

Following the end of treatment, participants will be reviewed at 12, 24, 36 and 48-weeks post-treatment (SVR12, SVR24, SVR36 and SVR48). At follow-up visits, HCV RNA will be measured using the Xpert® HCV Viral Load assay. If HCV RNA is detected at a follow-up visit, local laboratory HCV RNA and genotype will be measured to determine re-infection.

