10.2 Dosing and Administration

Participants should be instructed to take study medication with food at approximately the same time each day. Dose modifications are prohibited. The first study drug dosing will commence in hospital at Baseline (day 0). The start date and the last dose of the regimen should be documented in the subject's source documents and appropriate eCRF.

Participants should be instructed to swallow the study drug tablets whole. Participants should be instructed to only remove the tablets from the packaging immediately prior to dosing.

For a missed dose of study drug, participants should be instructed to take the missed dose of study drug as soon as possible during the same day. However, no more than the daily dose of sofosbuvir and glecaprevir/pibrentasvir should be taken on any calendar day. Participants should be cautioned never to double the next dose with a missed dose of study drug under any circumstances.

Dispensing

Participants will be dispensed with their study medication daily prior to hospital discharge. At the hospital discharge visit, participants will be dispensed with the remaining study medication for the treatment regimen. Participants should receive counseling on the importance of adherence in regard to virologic response and potential development of resistance.

Adherence

Adherence monitoring will be daily observed, and the date and time will be recorded in the medical records prior to hospital discharge. Following hospital discharge, participants will be contacted weekly for self-reported treatment adherence.

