10.3 Prior and concomitant medications

The prescribing information for all concomitant drugs should be consulted and reviewed carefully. The determinations listed in the respective contraindicated, warning, and precaution sections must be respected in order to prevent any potentially serious and/or life-threatening drug interactions.

Drug-drug interactions for each participant should be assessed on <http://www.hep-druginteractions.org/>. In case of any questions on potential interactions with a drug, please contact the study principal investigator.

Use of medications listed below within 2 weeks or 10 half-lives, whichever is longer, prior to study drug administration is contra-indicated (see Tables 1 and 2):

Table 2 Contraindicated concomitant medications with glecaprevir/pibrentasvir

Drug Class	Drug(s) within Class that are Contraindicated	Clinical Comments
Anticoagulants	Dabigatran	May increase dabigatran concentration potentially increasing risk of bleeding
Anticonvulsants	Carbamazepine	May decrease DAA exposure leading to a potential loss of therapeutic activity.
Antimycobacterial	Rifampin	May decrease DAA exposure leading to a potential loss of therapeutic activity.
Ethinyl estradiol-containing products	Ethinyl estradiol-containing medications (such as combined oral contraceptives and hormone replacement therapy)	Potential for ALT elevation
Gastrointestinal pro-kinetic agent	Cisapride	
Herbal Product	St. John's Wort (Hypericum perforatum)	May decrease DAA exposure leading to a potential loss of therapeutic activity.
HIV non-nucleoside reverse transcriptase inhibitor	Efavirenz Etravirine Nevirapine	May decrease DAA exposure leading to a potential loss of therapeutic activity.
HIV protease inhibitor	Atazanavir Darunavir	Potential for ALT elevation
HMG-CoA Reductase Inhibitors *	Atorvastatin Lovastatin Simvastatin	Potential for myopathy including rhabdomyolysis.

Immunosuppressant	Cyclosporin	Co-administration not recommended with cyclosporin dose >100mg per day
-------------------	-------------	--

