* Some HMG-CoA reductase inhibitors (including atorvastatin, lovastatin, or simvastatin) should not be taken with glecaprevir/pibrentasvir. Participants receiving these statins should either switch to pravastatin or rosuvastatin prior to the first dose of study drug or interrupt statin therapy throughout the treatment period and until 30 days after the last dose. If switching to or continuing pravastatin or rosuvastatin, it is recommended to reduce the pravastatin dose by 50% or limit the rosuvastatin dose to 10 mg daily while on treatment.

Table 3 Contraindicated concomitant medications with sofosbuvir

Drug Class	Drug(s) within Class that are contraindicated	Clinical Comments
Analeptics	Modafinil	Coadministration of sofosbuvir with modafinil is expected to decrease the concentration of sofosbuvir, leading to reduced therapeutic effect of sofosbuvir. Such coadministration is not recommended.
Antiarrhythmics	Amiodarone	Coadministration of amiodarone with another direct acting antiviral may result in symptomatic bradycardia. If coadministration is required, cardiac monitoring is recommended.
Anticoagulants	Vitamin K agonists	Close monitoring of the INR is recommended, as liver function may change with sofosbuvir treatment.
Anticonvulsants	Carbamazepine Phenytoin Phenobarbital Oxcarbazepine	May decrease DAA exposure leading to a potential loss of therapeutic activity, therefore not recommended.
Antimycobacterials	Rifabutin Rifampin Rifapetine	May decrease DAA exposure leading to a potential loss of therapeutic activity, therefore not recommended.
Herbal Supplements	St John's wort	May decrease DAA exposure leading to a potential loss of therapeutic activity, therefore not recommended.
HIV Protease Inhibitors	Tipranavir Ritonavir	May decrease DAA exposure leading to a potential loss of therapeutic activity, therefore not recommended.

11 Study procedures

Screening Visit (Week -6 to Week 0) – All participants

- Informed consent: At the screening visit, participants will provide written and informed consent prior to any study-specific procedures.
- Medical history: A medical history will be taken
- Physical measurements: Height and body weight.
- Clinical laboratory tests: At a minimum, liver function tests, biochemistry and full blood count tests will be collected at Screening (or used from admission bloods).
- HCV RNA (local laboratory): Quantitative HCV RNA

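### After discharge on treatment, the weekly contact is specified for adherence only; adding a medicines question would shorten the gap between interaction checks (low-priority improvement, both cohorts)

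*Protocol*

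**What the plan says.** The weekly post-discharge contact is described in three places, each time for adherence alone:

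- Footnote 7 to both schedules of assessments (sections 3 and 4): "Study drug adherence will be collected via telephone on a weekly basis for participants who are discharged prior to treatment completion".
- Section 9.2: discharged patients "receive weekly contact to measure treatment adherence".
- Section 10.2: "Following hospital discharge, participants will be contacted weekly for self-reported treatment adherence".

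Medicines are handled separately. Footnote 6 says: "Concomitant medications will be assessed at Screening and updated at visits as appropriate". In the Cohort B schedule the concomitant-medication row is marked at Screening, Baseline, Hospital discharge, End of Treatment (Week 4) and SVR12. Cohort A has the same marks plus Week 4, with End of Treatment at Week 8.

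Section 10.2 also states: "At the hospital discharge visit, participants will be dispensed with the remaining study medication for the treatment regimen". Section 10.3 sets the rules on interacting drugs ("The determinations listed in the respective contraindicated, warning, and precaution sections must be respected") and names an interaction website. It gives no timing for a check after discharge.

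**The concern.** A new medicine may be started after discharge by someone outside the study team. The study speaks to the patient every week in that period, but the planned content of the contact does not include medicines. After a planned discharge the patient already holds the rest of the course, so there is no later dispensing contact at which a new drug would be noticed.

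For rifampin, carbamazepine and others, Table 2 gives the consequence as "May decrease DAA exposure leading to a potential loss of therapeutic activity". Other listed drugs carry a risk of harm while dosing continues: dabigatran (bleeding, Table 2) and, with sofosbuvir in Cohort B, amiodarone (bradycardia, Table 3). In Cohort B, a listed drug started after discharge is first looked for when dosing is over and the course can no longer be protected. In Cohort A the same drug could go unlooked-for over the second half of treatment. Section 15.2 also has a secondary safety endpoint on the rates and predictors of interaction-related adverse events. Earlier and better-dated capture of new medicines would help that endpoint.

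**Working it through.** The protocol states no figure to reproduce. The check is a reading of the schedules followed by subtraction.

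**Inputs.** End of Treatment is day 28 in Cohort B and day 56 in Cohort A, with a Week 4 visit on day 28 in Cohort A (sections 3 and 4). A medicines check is scheduled at the discharge visit itself, so the gap starts there. Let d be the treatment day of discharge; its values below are illustrations.

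**Formulas.**
- Cohort B: gap = max(0, 28 − d).
- Cohort A, d up to 28: gap to Week 4 = 28 − d, then 56 − 28 = 28 days to Week 8.
- Cohort A, d after 28: gap to Week 8 = max(0, 56 − d).

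| d | Cohort B, to End of Treatment | Cohort A, to Week 4 | Cohort A, to Week 8 |
|---|---|---|---|
| 7 | 21 | 21 | then 28 |
| 14 | 14 | 14 | then 28 |
| 21 | 7 | 7 | then 28 |
| 28 | 0 | 0 | then 28 |
| 42 | 0 | none | 14 |
| 56 | 0 | none | 0 |

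**By length of stay.** The background section cites a mean stay of 12 days in one audit and intravenous treatment of 2 to 6 weeks for many of these infections. It expects HCV treatment to start early in the admission. Assume dosing starts on admission day 3 (range 1 to 5), so d = stay − start day.
- 12-day stay: d = 12 − 3 = 9; Cohort B gap 28 − 9 = 19 days (17 to 21).
- 14-day stay: d = 11; gap 17 days (15 to 19).
- 28-day stay: d = 25; gap 3 days (1 to 5).
- 42-day stay: d = 39; no gap in Cohort B; Cohort A gap 56 − 39 = 17 days (15 to 19).

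The Cohort B gap is therefore material for stays of about two weeks and small or absent for stays of four to six weeks. Cohort A has the longest fixed gap, 28 days, for anyone discharged by Week 4.

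**What the calls add.** Count weekly calls from discharge to End of Treatment, leaving out day 28 in Cohort A because it is a visit.
- d = 7: Cohort A days 14, 21, 35, 42, 49 (5 calls); Cohort B days 14, 21 (2 calls).
- d = 14: Cohort A days 21, 35, 42, 49 (4 calls); Cohort B day 21 (1 call).
- d = 21 or 28: Cohort A days 35, 42, 49 (3 calls); Cohort B none.

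With a medicines question on each call, the longest planned gap after discharge is about 7 days, provided the calls are answered. In Cohort B a patient discharged on day 21 or later gains nothing, because the next weekly point is already End of Treatment.

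**The case against.** The strongest reply is that nothing here is wrong. The protocol is consistent: adherence is asked weekly, medicines are reviewed at visits, and no text forbids asking about medicines on a call. Checks already take place at Screening, Baseline, discharge, Week 4 (Cohort A), End of Treatment and SVR12. Patients are followed in viral hepatitis services, and records may reveal a new drug. A medicine started after discharge can still be recorded later, at End of Treatment or SVR12, so it is not shown that endpoint data would be lost. The protocol gives no rate of new interacting prescriptions. Calls may go unanswered, and self-report may be unreliable.

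Most of this stands, and it sets the priority: an optional improvement of low rank. It does not remove the gap. Recording a drug at End of Treatment documents it but cannot protect a course that is over, and outpatient care and records are not scheduled checks.

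Four stronger readings are tempting, and the documents do not support them.
- A reader might infer that interacting drugs are ungoverned once dosing starts. They are not: section 10.3 requires product warnings to be respected and has patients on certain statins switch or "interrupt statin therapy throughout the treatment period and until 30 days after the last dose". What is missing is a scheduled check to find a newly started drug.
- A reader might infer that this is a Cohort B problem. The longest fixed gap and most of the added calls are in Cohort A.
- A reader might infer that Cohort A always has a gap. It has none once discharge falls on or after treatment day 56.
- A reader might infer that no further supply contact can occur. After an unplanned discharge, section 9.4 has the nurse attempt contact and help with access to drug. It names no medicines check, and the content of the Early Discharge CRF is not shown.

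**Conclusion.** The point holds as a cheap, low-priority improvement. After discharge on treatment, no interaction check is scheduled until the next visit. In Cohort B the gap is 28 minus the treatment day of discharge, and it ends when dosing ends. In Cohort A, patients discharged by Week 4 have the same first gap and then 28 days to Week 8; those discharged later have a shorter gap or none.

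The gaps in days follow from the schedules. The stay-length figures also rest on the assumed start of dosing on admission day 3 (range 1 to 5). The gain to about 7 days depends on answered calls and reasonable self-report. No number of affected patients can be given, and nothing here bears on the primary analysis.

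**What to change.** Amend footnotes 6 and 7 in both schedules, and sections 9.2 and 10.2, so that each weekly call also asks whether any medicine has been started, stopped or changed. Check any reported change against Tables 2 and 3 and the interaction website, and refer a listed drug promptly to the treating clinician. Confirm from medical or pharmacy records only when a listed drug is reported. Ask the same question at the nurse contact in section 9.4.

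Cost: a minor amendment needing ethics approval (section 19), best bundled with another; slightly longer calls; and a short eCRF entry (drug, change, dates) when a change is reported. No extra visit is needed. If all 30 patients per cohort were discharged on the same treatment day, the calls would number 30 × (5 + 2) = 210 for day 7, 30 × (4 + 1) = 150 for day 14, and 30 × (3 + 0) = 90 for day 21 or 28. At an assumed 3 extra minutes per call that is 10.5, 7.5 and 4.5 staff hours; at 6 minutes it is 21, 15 and 9. Checking and referring a reported drug, and confirming it from records, takes further time that is not counted here.

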7.1 Primary objective

- To evaluate the proportion of patients achieving confirmed SVR12 (undetectable HCV RNA at time point 12 weeks plus post treatment commencement) in hospitalized patients commencing inpatient DAA treatment within public hospital services

7.2 Secondary Objectives

- To evaluate the proportion of patients achieving confirmed SVR12 (undetectable HCV RNA at time point 12 weeks plus post treatment commencement) in patients hospitalised for IRID and commencing inpatient DAA treatment within public hospital services
 - To evaluate and compare the proportion of patients with undetectable HCV RNA at 12 weeks post-treatment (SVR12) within each cohort
 - To evaluate proportion of patients with HCV below LLOQ at week 4 of therapy and ETR
 - To evaluate DAA treatment completion rates
 - To evaluate adherence during treatment via in hospital medication charts and outpatient weekly self-report
 - To evaluate acceptability and feasibility of DAA commencement whilst an inpatient
 - To evaluate adverse events secondary to drug:drug interactions
 - To evaluate performance of finger prick POC testing compared to plasma HCV RNA at screening
 - To evaluate completion of duration of recommended inpatient stay and therapy for co-morbidities
 - To determine effect of HCV treatment on quality of life
 - To evaluate rate of re-call and re-infection at 6, 9- and 12-months post study enrolment
- In those who inject drugs:
- To evaluate engagement with D&A services and rates of OST initiation
 - To determine rates and patterns of injecting behaviour following therapy for HCV

8 Participant population

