8.2 Inclusion criteria

Participants must meet all of the following inclusion criteria to be eligible to participate in this study.

- 1) Have voluntarily signed the informed consent form.
- 2) 18 years of age or older.
- 3) Injected drugs within the last 6 months OR be known to be HCV Ab positive
- 4) Hospitalized with an IRI with an anticipated inpatient stay of > 1 weeks¹
- 5) HCV RNA positive
- 6) Compensated liver disease
- 7) Documented non-cirrhotic at enrolment with a qualifying liver FibroScan ≤ 9.5 kpA or an APRI < 2.0
- 8) If co-infection with HIV is documented, the subject must meet the following criteria:
 - a. ART naïve with CD4 T cell count >500 cells/mm³;
OR
 - b. On a stable ART regimen (containing only permissible ART) for >4 weeks prior to screening visit, with CD4 T cell count ≥ 200 cells/mm³ and a plasma HIV RNA level below the limit of detection. Permissible ARTs include:
 - Raltegravir
 - Dolutegravir
 - Rilprvirine
 - Elvitegravir/cobicistat
 - Tenofovir disproxil fumerate
 - Tenofovir alafenamide

- Emtricitabine
- Lamivudine
- Abacavir

¹ Although people who inject drugs are the focus of this study, patients without a recent history of IDU or IRID who are admitted with an expected duration of stay > 1 week may also be included at discretion of study team. In this case the questions on injecting behaviour will be omitted and additional data collected on nature of co-morbidities present.

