- HCV Genotype (local laboratory): HCV genotype should be collected at screening. Historical participant genotype results are acceptable if these were conducted within 5 years from Screening.
- HCV RNA (point-of-care): A finger-stick capillary whole-blood sample will be collected for the GeneXpert. This may be repeated if an invalid result is obtained in the absence of a local laboratory HCV RNA.

- HIV and HBV serology: Anti-HIV Ab and HBsAg results within 5 years prior to Screening are also acceptable.
- Fibrosis Assessment: Liver fibrosis will be measured using a FibroScan where possible. An AST to Platelet Ratio Index (APRI) will be considered as an acceptable alternative if a FibroScan is not possible.
- Pregnancy test: All females of child-bearing potential will have a serum or urine pregnancy test. This will not be required for females of non-childbearing potential. Determination of postmenopausal status will be recorded during the Screening period based on participant history.
- Behavioural survey and EQ-5D-5L.
- Clinical assessment and concomitant medication assessment / DDI assessment.
- Dried Blood Spot sample.

The following study visits are for participants who commence treatment only.

Baseline visit (Week 0)

Eligible participants who meet the treatment inclusion criteria and meet none of the exclusion criteria will proceed to the baseline visit. This visit must be completed prior to hospital discharge.

The following procedures will be conducted:

- Concomitant medications / DDI assessment: These will be updated from the Screening visit as necessary.
- Pregnancy test: Urine or serum pregnancy tests.
- Full blood count and biochemistry
- Treatment initiation: Participants will be administered the study drug at the site with dosing instructions at the baseline visit.

Week 4 (Cohort A only)

Participants in Cohort A will have an on-treatment visit at Week 4. The following procedures will be conducted:

- HCV RNA testing (local laboratory)
- Pregnancy test (women of child-bearing potential; serum or urine)
- Concomitant medication assessment / DDI assessment
- Adherence

End of Treatment – (Week 8 – Cohort A, Week 4 – Cohort B)

The date of the last dose of study medication will be collected. The end of treatment visit will be either Week 8 or Week 4, depending on the cohort. The following procedures will be conducted:

- HCV RNA testing (local laboratory)
- Liver function tests

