- Pregnancy test (women of child-bearing potential; serum or urine)
- Concomitant medication assessment / DDI assessment
- Adherence

Follow-up Visits (SVR12, SVR24, SVR36 and SVR48)

Participants will return for follow-up visits every 12 weeks after the last dose of study medication.

All participants will have the following procedures conducted:

- HCV RNA testing (local laboratory or point of care)
- Behavioural survey and EQ-5D-5L: Participants will complete this questionnaire at SVR12 and SVR48.
- Liver function tests
- Concomitant medication assessment / DDI assessment (SVR12 only)

If a participant is found to be HCV RNA positive at SVR12, additional procedures will be conducted to determine re-infection/relapse. These procedures are:

- HCV Genotype
- Dried Blood Spot Sample for sequencing
- EDTA Plasma for resistance testing (10mL)

All on-treatment visits will be conducted whilst the participant is still an in-patient. If the participant is discharged prior to treatment completion, visits will be conducted through outpatient viral hepatitis services.

Questionnaires

Health Outcomes Survey (EQ-5D-5L)

The EQ-5D-5L provides a simple descriptive profile and a single index value for health status. This information can then be translated into a health utility, which can be used for cost-effectiveness analyses.

Behavioural Questionnaire

Participants will complete a behavioural questionnaire at Screening, SVR12 and SVR48. The behavioural questionnaire will collect information on demographics, drug and alcohol usage, injecting risk behaviours.

12 Recording and reporting Adverse Events (AEs)

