15.2 Secondary Endpoints

- Proportion of patients with HCV RNA below the level of detection at 12 weeks post-treatment (SVR12) within each cohort by both ITT and PP analyses
- Proportion of patients with HCV below LLOQ at week 4 of therapy and ETR
- Proportion of patients completing DAA treatment course
- Proportion of patients with full (100%) and partial adherence (<50%, 50-80%, 81-99%) during treatment as assessed by in hospital medication charts and outpatient weekly self-report
- Uptake of DAA therapy during admission in patients suitable for study
- Safety: Rates and predictors of adverse events secondary to drug:drug interactions
- Sensitivity and specificity of finger prick POC testing compared to plasma HCV RNA at screening
- Proportion of patients completing recommended inpatient stay
- Changes in HRQOL
- Rates of re-attendance at subsequent planned study visits
- Rates and predictors of reinfection during follow-up

In those with a history of injecting drug use:

- Proportion of patients undergoing D&A evaluation during admission
- Proportion of patients initiating OST during admission
- Frequency and patterns of injecting behaviour following therapy for HCV

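### The quality-of-life objective claims an effect of HCV treatment, but the only pre-treatment EQ-5D-5L is taken during the hospital admission and there is no untreated comparator, so the change cannot be attributed to treatment

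*Protocol*

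**What the plan says.** The objective, in Protocol Section 7.2 and in the synopsis, is "To determine effect of HCV treatment on quality of life". The matching endpoint in Section 15.2 is only "Changes in HRQOL", with no contrast or comparator named.

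The timing of the questionnaire is fixed in Sections 3, 4 and 11:

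- **Before treatment.** "Behavioural survey and EQ-5D-5L" is in the Screening list in Section 11. The Baseline list has no questionnaire.
- **After treatment.** "Participants will complete this questionnaire at SVR12 and SVR48" (Section 11, Follow-up Visits).
- **Setting.** Section 9.2 states "Participants will be invited for Screening whilst they are inpatients of the hospital". Section 11 also requires the Baseline visit to be completed before discharge.
- **Population.** The admission criterion in Section 8.2 is "Hospitalized with an IRI with an anticipated inpatient stay of > 1 weeks". Its footnote adds that "patients without a recent history of IDU or IRID who are admitted with an expected duration of stay > 1 week may also be included".

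Section 9.1 describes an open-label, single-arm study of two sequential cohorts, both receiving antiviral treatment.

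**The concern.** The objective is causal, while the endpoint and the design are not. A before-after difference can stand for a treatment effect only if little else that bears on the outcome changes over the interval. Here the starting value is taken when the participant is ill enough to be in hospital with an expected stay of more than a week. The next value comes months later.

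A reported gain in EQ-5D-5L would answer the objective as written, and readers would credit it to HCV treatment. Much or all of it could be recovery from the admission. This is a matter for the protocol: an analysis plan cannot create an untreated group, or a pre-treatment measurement outside the admission.

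**Working it through.** The protocol states no effect size, standard deviation or power for quality of life, so there is no figure to reproduce. The question is whether the planned data can identify the stated effect.

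**Step 1. When EQ-5D-5L is measured (Sections 3, 4 and 11).**

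| Visit | Cohort A, study week | Cohort B, study week | EQ-5D-5L |
|---|---|---|---|
| Screening (inpatient) | up to 0 | up to 0 | yes |
| Baseline | 0 | 0 | no |
| Hospital discharge | variable | variable | no |
| Week 4 on treatment | 4 | (is End of Treatment) | no |
| End of Treatment | 8 | 4 | no |
| SVR12 | 8 + 12 = 20 | 4 + 12 = 16 | yes |
| SVR24, SVR36 | 32, 44 | 28, 40 | no |
| SVR48 | 8 + 48 = 56 | 4 + 48 = 52 | yes |

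**Step 2. How the interval compares with the admission.** Section 5 says that many of these infections need two to six weeks of inpatient intravenous treatment. It also cites a single-centre audit with an average stay of 12 days. The first post-treatment questionnaire falls 16 × 7 = 112 days (Cohort B) or 20 × 7 = 140 days (Cohort A) after treatment starts. Most participants would be expected to have left hospital by then.

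**Step 3. What the change contains.** For a participant, write

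change from Screening to SVR12 = R + D + T

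where R is recovery from the admitting illness and its treatment, D is the effect of discharge and of any drug and alcohol care or opioid substitution, and T is the effect of HCV treatment. D is not idle speculation: hypothesis 4 in Section 6 expects better engagement with drug and alcohol services, and Section 15.2 counts participants who start opioid substitution during the admission.

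Only the sum is observed. If T = 0, the change is R + D, which would be expected to be positive. A larger sample estimates the sum more precisely and does not split it.

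**Step 4. Whether anything else in the design isolates T.**

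- *Change to SVR48.* It uses the same inpatient starting value, so R and D remain.
- *Cohort A against Cohort B.* Both are treated, the cohorts are enrolled one after the other, and the SVR12 visits differ by 20 − 16 = 4 weeks. The contrast cannot give the effect of treatment against none.
- *Historical comparison.* Hypothesis 1 in Section 6 names historical data for follow-up and SVR12 outcomes. None is named for quality of life.

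No planned contrast recovers T.

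**The case against.** The strongest reply is that this is one of many secondary objectives in a study of 60 with no formal sample size, that every single-arm study lacks a control, that the endpoint is already descriptive, and that Section 15.3 leaves the detailed analysis to a later plan. Most of this is true and limits the weight of the point. It does not remove it, because the stated objective still asks for an effect that the fixed schedule and design cannot supply.

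The objection is right to bar several stronger readings that a reader might infer:

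- **That the trial is certain to show improvement, or that a given share of the gain is recovery.** The protocol contains no EQ-5D-5L values or trajectories, and it describes a group with high morbidity and competing priorities. Improvement is to be expected but not assured, and any percentage would only restate assumed utilities.
- **That every participant has an acute infection.** The footnote to Section 8.2 admits others. They too are inpatients expected to stay more than a week, so the argument still applies.
- **That the error will pass into a cost-effectiveness analysis.** Section 11 says only that the instrument can serve such analyses. No economic objective, endpoint or analysis is planned.
- **That change from End of Treatment to SVR12 would isolate the effect.** End of Treatment follows the full antiviral course, so any on-treatment effect is already in the reference. In Cohort B it falls at week 4, inside the two-to-six-week range for intravenous treatment, and Section 4 places the visit in hospital where possible.
- **That SVR12 achievers against non-achievers would do so.** Section 5 cites SVR above 95% for eight weeks of the dual regimen. If that held in both cohorts (an assumption), fewer than 0.05 × 60 = 3 participants would be virological failures. Those counted as failures because they missed SVR12 would have no questionnaire from that visit, and the groups would also differ in adherence and retention.

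**Conclusion.** The point holds: the wording of the Section 7.2 objective goes beyond what the design can show. The change in EQ-5D-5L from Screening to SVR12 or SVR48 is confounded by recovery from the admitting illness, by discharge, and by any drug and alcohol care or opioid substitution. The HCV treatment component cannot be identified at any sample size.

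The conclusion rests on the fixed visit schedule, the inpatient setting of Screening and the absence of an untreated comparator, all stated in the protocol. That improvement would be expected without any treatment effect rests on the ordinary assumption that people feel better after a serious admission than during it. The size of the bias is unknown. The change is also not proof that treatment has no effect: it is uninformative on that question. The consequence is confined to one secondary objective; the primary SVR12 endpoint is untouched.

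**What to change.** In Section 7.2 and the synopsis, restate the objective to match the endpoint: to describe EQ-5D-5L from inpatient Screening to SVR12 and SVR48. Add one sentence saying that the change cannot be attributed to HCV treatment and is not to be used as a treatment utility. This costs only the rewording.

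Optionally, add EQ-5D-5L at the existing hospital discharge and End of Treatment visits to chart recovery. The cost is one short form per visit and some missing data, for example after unplanned discharge or missed outpatient visits. Label these results descriptive, because they do not isolate a treatment effect, and note that in Cohort B the End of Treatment form may still be completed during the admission.

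A causal objective would need a concurrent hospitalised group without HCV treatment over the same interval, which is a different study and is not proposed here.
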